## 7.0 SUPPORTIVE CARE AND OTHER CONCOMITANT THERAPY

### 7.1 Concurrent Anticancer Therapy

Concurrent cancer therapy, including chemotherapy, radiation therapy, immunotherapy, or biologic therapy may NOT be administered to patients receiving study drug. If these treatments are administered the patient will be removed from protocol therapy.

### 7.2 Investigational Agents

No other investigational agents may be given while the patient is on study.

### 7.3 Supportive Care

Appropriate antibiotics, blood products, antiemetics, fluids, electrolytes and general supportive care are to be used as necessary. Please see COG Supportive Care guidelines at <https://childrensoncologygroup.org/index.php/cog-supportive-care-guidelines>. See [Section 7.5](#) for drugs that should not be used concomitantly due to potential interactions with erdafitinib. See below for recommendations on management of specific toxicities associated with erdafitinib.

#### 7.3.1 Nausea and vomiting:

Nausea and vomiting has been observed frequently in adult patients treated with erdafitinib. It is recommended to provide all patients a 5-HT3-Receptor blocker (e.g., ondansetron or granisetron) at the start of treatment to be used as needed or prophylactically. In the event of breakthrough nausea/vomiting, additional antiemetics may be added as needed.

#### 7.3.2 Mucositis:

For grade 1 mucositis, it is recommended to use conservative measures such as non-alcoholic mouth wash or salt water (0.9%) mouth wash several times a day until resolution. For grade  $\geq$  2 mucositis, topical analgesic mouth treatments (i.e., local

anesthetics such as benzocaine, butyl aminobenzoate, tetracaine hydrochloride, menthol, or phenol) may be used with or without topical corticosteroids, such as triamcinolone oral paste 0.1% (e.g. Kenalog in Orabase®). Agents containing hydrogen peroxide, iodine, and thyme derivatives may worsen mouth ulcers and should not be used.

Systemic antifungal agents should be avoided unless a fungal infection is diagnosed. In particular, systemic imidazole antifungal agents (ketoconazole, fluconazole, itraconazole, voriconazole, etc.) should be avoided due to their strong inhibition of CYP3A4 metabolism, therefore leading to higher erdafitinib exposure. Topical antifungal agents are preferred if an infection is diagnosed.

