## 4.0 PATIENT ELIGIBILITY

All clinical and laboratory studies to determine eligibility must be performed within 7 days prior to enrollment unless otherwise indicated. Laboratory values used to assess eligibility must be no older than seven (7) days at the start of therapy. Laboratory tests need **not** be repeated if therapy starts **within** seven (7) days of obtaining labs to assess eligibility. If a post-enrollment lab value is outside the limits of eligibility, or laboratory values are older than 7 days, then the following laboratory evaluations must be re-checked within 48 hours prior to initiating therapy: CBC with differential, bilirubin, ALT (SGPT) and serum creatinine. If the recheck is outside the limits of eligibility, the patient may not receive protocol therapy and will be considered off protocol therapy. Imaging studies, bone marrow biopsy and/or aspirate (when applicable) must be obtained within 14 days prior to start of protocol therapy (repeat the tumor imaging if necessary).

Clarification in timing when counting days: As an example, please note that if the patient's last day of prior therapy is September 1st, and the protocol requires waiting at least 7 days for that type of

prior therapy, then that patient cannot be enrolled until September 8th.

**Important note: The eligibility criteria listed below are interpreted literally and cannot be waived. All clinical and laboratory data required for determining eligibility of a patient enrolled on this trial must be available in the patient's medical or research record which will serve as the source document for verification at the time of audit.**

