#### 4.2.2.4 Anti-GVHD agents post-transplant:

Patients who are receiving cyclosporine, tacrolimus or other agents to prevent graft-versus-host disease post bone marrow transplant are not eligible for this trial.

4.2.2.5 CYP3A4 Agents: Patients who are currently receiving drugs that are strong inducers or inhibitors of CYP3A4 are not eligible. See [Appendix](#)

[II](#) for a list of agents. Note: CYP3A4 inducing anti-epileptic drugs and dexamethasone for CNS tumors or metastases, on a stable dose, are allowed.

4.2.2.6 CYP2C9 Agents: Patients who are currently receiving drugs that are strong inducers or moderate inhibitors of CYP2C9 are not eligible. See [Section 7.5.2](#).

- 4.2.3 Infection: Patients who have an uncontrolled infection are not eligible.
- 4.2.4 Patients who have received a prior solid organ transplantation are not eligible.
- 4.2.5 Patients who in the opinion of the investigator may not be able to comply with the safety monitoring requirements of the study are not eligible.
- 4.2.6 A history of cardiovascular diseases: Unstable angina, myocardial infarction, or known congestive heart failure Class II-IV within the preceding 12 months; cerebrovascular accident or transient ischemic attack within the preceding 3 months, pulmonary embolism within the preceding 2 months.
- 4.2.7 A history of any of the following: sustained ventricular tachycardia, ventricular fibrillation, Torsades de Pointes, cardiac arrest, Mobitz II second degree heart block or third degree heart block; known presence of dilated, hypertrophic, or restrictive cardiomyopathy.
- 4.2.8 Uncontrolled intercurrent illness including, but not limited to, ongoing or active infection, symptomatic congestive heart failure, unstable angina pectoris, cardiac arrhythmia, or psychiatric illness/social situations that would limit compliance with study requirements.
- 4.2.9 Patients with significant ophthalmologic conditions (uncontrolled glaucoma, central serous retinopathy, history of retinal vein occlusion or retinal detachment, excluding patients with longstanding findings secondary to existing conditions) are not eligible, to be confirmed with baseline ophthalmologic exam. All patients must have a baseline ophthalmologic exam, including funduscopy to confirm no significant ophthalmologic conditions are present.

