#### 7.5 Concomitant Medications

- 7.5.1 CYP3A4 inhibitors or inducers: Strong CYP3A4 inhibitors or inducers are not permitted on study (See [Appendix II](#) for list of agents). Note: CYP3A4 inducing anti-epileptic drugs and dexamethasone for CNS tumors or metastases, on a stable dose, are allowed. No grapefruit juice, Seville oranges, or grapefruit can be consumed while on erdafitinib.
- 7.5.2 CYP2C9 inhibitors or inducers: Moderate CYP2C9 inhibitors or strong CYP2C9 inducers are not permitted on the study.
- 7.5.3 CYP3A4 substrates: Until further data become available, concomitant use of erdafitinib with CYP3A4 substrates with narrow therapeutic indices should be avoided.
- 7.5.4 Co-administration of erdafitinib with other serum phosphate altering agents may affect serum phosphate concentrations. Avoid co-administration of serum phosphate altering agents if reasonable alternatives exist.
- 7.5.4 Concomitant administration of erdafitinib with P-glycoprotein (P-gp) substrates may increase their systemic exposure if administered concurrently.
- 7.5.5 P-glycoprotein: Concomitant administration of erdafitinib with P-glycoprotein (P-gp) substrates may increase their systemic exposure if administered concurrently. Oral narrow therapeutic index P-gp substrates such as digoxin should be taken at least 6 hours before or after erdafitinib to minimize the potential for interactions
- 7.5.6 OCT2: Erdafitinib was shown to be an OCT2 inhibitor in vitro. Until further data are available, consider alternative agents that are not OCT2 substrates. Metformin is an example of an OCT2 substrate.

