### **Potential Drug Interactions**

Erdafitinib is a weak time-dependent inhibitor and weak inducer of CYP3A4. Until further data become available, concomitant use of erdafitinib with CYP3A4 substrates with narrow therapeutic indices should be avoided.

Co-administration with a moderate CYP2C9 or strong CYP3A4 inhibitor increased erdafitinib exposure and may lead to increased drug-related toxicity. The use of moderate inhibitors of CYP2C9 and strong inhibitors of CYP3A4 are not permitted for the duration of the study.

The impact of strong CYP2C9 or CYP3A4 inducers (such as rifampin) on erdafitinib was not clinically studied. The concomitant use of strong CYP2C9 and CYP3A4 inducers with erdafitinib should be avoided as co-administration may significantly decrease erdafitinib exposure. Caution should be exercised for concomitant administration of erdafitinib and moderate CYP2C9 or CYP3A4 inducers as this may result in decreased erdafitinib exposure.

Co-administration of erdafitinib with other serum phosphate altering agents may affect serum phosphate concentrations. Avoid co-administration of serum phosphate altering agents if reasonable alternatives exist.

Concomitant administration of erdafitinib with P-glycoprotein (P-gp) substrates may increase their systemic exposure if administered concurrently. Oral narrow therapeutic index P-gp substrates such as digoxin should be taken at least 6 hours

before or after erdafitinib to minimize the potential for interactions.

Erdafitinib was shown to be an OCT2 inhibitor in vitro. PK simulations with metformin, an OCT2 substrate, predicted a lack of clinically relevant interaction with erdafitinib. However, until further data are available, consider alternative therapies that are not OCT2 substrates.

No clinically significant QT prolongation or cardiovascular effects have been noted to date. Clinical trials revealed no effects of erdafitinib on cardiac repolarization or other electrocardiographic parameters.

Acid lowering agents (e.g., antacids, H2-antagonists, or proton pump inhibitors) are not expected to affect the bioavailability of erdafitinib. Erdafitinib may be co-administered with an acid lowering agent.

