**APPENDIX II: CYP3A4 SUBSTRATES, INDUCERS AND INHIBITORS**

This is not an inclusive list. Because the lists of these agents are constantly changing, it is important to regularly consult frequently updated medical references.

CYP3A4 substrates	Strong Inhibitors	Moderate Inhibitors	Strong Inducers	Moderate Inducers
acalabrutinib 	atazanavir	aprepitant	barbiturates	bosentan
alfentanil 	boceprevir	conivaptan	carbamazepine	dabrafenib
amiodarone 	clarithromycin	crizotinib	enzalutamide	efavirenz
aprepitant/fosaprepitant	cobicistat	diltiazem	fosphenytoin	etravirine
atorvastatin	darunavir	dronedarone	phenobarbital	modafinil
axitinib	delavirdine	erythromycin	phenytoin	nafcillin
bortezomib	grapefruit 	fluconazole	primidone	rifapentin
bosutinib 	grapefruit juice 	fosamprenavir	rifampin	
budesonide 	idelalisib	grapefruit 	St. John's wort	
bupirone 	indinavir	grapefruit juice 		
cabozantinib	itraconazole	imatinib		
calcium channel blockers	ketoconazole	isavuconazole		
cisapride	lopinavir/ritonavir	mifepristone		
citalopram/escitalopram	nefazodone	nilotinib		
cobimetinib 	nelfinavir	verapamil		
conivaptan 	posaconazole			
copanlisib	ritonavir			
crizotinib	saquinavir			
cyclosporine 	telaprevir			
dabrafenib	telithromycin			
dapsone	voriconazole			
darifenacin 				
darunavir 				
dasatinib 				
dexamethasone 				
diazepam				
dihydroergotamine				
docetaxel				
doxorubicin				
dronedarone 				
eletriptan 				
eplerenone 				
ergotamine 				
erlotinib				
estrogens				
etoposide				

everolimus  fentanyl  gefitinib haloperidol ibrutinib  idelalisib imatinib indinavir  irinotecan isavuconazole  itraconazole ivacaftor ketoconazole lansoprazole lapatinib losartan lovastatin  lurasidone  macrolide antibiotics maraviroc  medroxyprogesterone methadone midazolam  midostaurin  modafinil nefazodone nilotinib olaparib ondansetron osimertinib paclitaxel palbociclib pazopanib quetiapine  quinidine  regorafenib romidepsin saquinavir  sildenafil  simvastatin 				
---	--	--	--	--

sirolimus 				

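### The CYP2C9 rules bar moderate inhibitors without naming strong ones, and Section 7.3.2 calls fluconazole a strong CYP3A4 inhibitor where Appendix II lists it as moderate

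*Combined protocol and SAP*

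**What the plan says.** **CYP2C9.** The eligibility rule in Section 4.2.2.6 reads "Patients who are currently receiving drugs that are strong inducers or moderate inhibitors of CYP2C9 are not eligible". The on-study rule in 7.5.2 reads "Moderate CYP2C9 inhibitors or strong CYP2C9 inducers are not permitted on the study". The agent section, 9.1.1 (Potential Drug Interactions), reads "The use of moderate inhibitors of CYP2C9 and strong inhibitors of CYP3A4 are not permitted for the duration of the study" and gives the reason: "Co-administration with a moderate CYP2C9 or strong CYP3A4 inhibitor increased erdafitinib exposure and may lead to increased drug-related toxicity". Section 4.0 says that the eligibility criteria are "interpreted literally and cannot be waived".

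**CYP3A4 and fluconazole.** Section 4.2.2.5 reads "Patients who are currently receiving drugs that are strong inducers or inhibitors of CYP3A4 are not eligible" and sends the reader to Appendix II. Section 7.5.1 sets the same strong-only limit on study, also by reference to Appendix II. Within the mucositis guidance, 7.3.2 says that "systemic imidazole antifungal agents (ketoconazole, fluconazole, itraconazole, voriconazole, etc.) should be avoided due to their strong inhibition of CYP3A4 metabolism". Appendix II puts ketoconazole, itraconazole and voriconazole in its strong-inhibitor column and fluconazole in its moderate-inhibitor column.

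**The concern.** A ban on the moderate members of a class would normally carry the strong members with it. Here the three CYP2C9 rules name only the moderate ones, and one of them is an eligibility criterion that the protocol itself says must be read to the letter. Section 9.1.1 attributes more of erdafitinib's clearance to CYP2C9 (39%) than to CYP3A4 (20%), so the larger pathway has the less complete rule.

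For fluconazole, two parts of the protocol disagree on its class, and that class decides whether the CYP3A4 bans apply. A site that reads 7.3.2 will take fluconazole to be strong and therefore prohibited. A site that goes from 7.5.1 to Appendix II will find it moderate and outside that ban. Section 7.3 points forward to 7.5 for drugs to avoid, but 7.5 does not point back to the azole advice in 7.3.2. The question is likely to come up, since oral mucositis is in the most frequent category (over 20%) of the adverse event list in 9.1.2.

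What is at stake is avoidable drug exposure in children, for whom Section 2.3.1 reports no earlier experience. No statistical quantity is involved.

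**Working it through.** The main check is a comparison of text.

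| Rule | CYP3A4 inhibitors barred | CYP2C9 inhibitors barred |
|---|---|---|
| Eligibility (4.2.2.5, 4.2.2.6) | strong | moderate |
| On study (7.5.1, 7.5.2) | strong | moderate |
| Agent information (9.1.1) | strong | moderate |

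No other section bars strong CYP2C9 inhibitors. There is also no list to consult: 4.2.2.6 refers to 7.5.2, which names no agents, and Appendix II covers CYP3A4 only.

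| Azole | Reason given in 7.3.2 | Column in Appendix II | Within the strong-only CYP3A4 bans? |
|---|---|---|---|
| ketoconazole | strong | strong | yes |
| itraconazole | strong | strong | yes |
| voriconazole | strong | strong | yes |
| fluconazole | strong | moderate | no |

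Appendix II says it is not complete. That does not explain the mismatch, because fluconazole is on the list and is classified there.

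**Scale, for illustration only.** The documents give no inhibition figure for any named drug, so I assume that 50% to 80% of CYP2C9 activity is lost. With f the share of clearance and x the fraction inhibited, AUC ratio = 1/(1 − f·x). Section 9.1.1 reports dose-proportional exposure from 0.5 to 12 mg, so the adult-equivalent dose is 8 mg times that ratio.

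*Check against the protocol's own figure.* Section 7.6 predicts 50% more exposure with CYP2C9 \*3/\*3, a ratio of 1.5, which needs f·x = 1 − 1/1.5 = 0.333.
- If 39% is a share of total clearance, x = 0.333/0.39 = 0.855, which is possible.
- If 39% is a share of the 67% metabolic part, f = 0.39 × 0.67 = 0.261 and x = 0.333/0.261 = 1.28, which is impossible. Only the first reading fits.

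*CYP2C9, total-clearance reading (f = 0.39).*
- x = 0.5: 1/(1 − 0.195) = 1.242, or 9.94 mg
- x = 0.8: 1/(1 − 0.312) = 1.453, or 11.63 mg
- x = 1: 1/(1 − 0.39) = 1.639, or 13.11 mg

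*CYP2C9, metabolic reading (f = 0.261).* The same three values of x give 9.20, 10.11 and 10.83 mg.

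*CYP3A4, total-clearance reading (f = 0.20).* Complete inhibition gives 1/(1 − 0.20) = 1.25, or 10.0 mg.

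The adult MTD is stated as at least 12 mg (Section 2.4). These figures are at the nominal 4.7 mg/m². Below the 8 mg cap, rounding in Appendix IV multiplies them by 0.86 (3 mg at 0.74 m² = 4.05 mg/m²) to 1.20 (3 mg at 0.53 m² = 5.66 mg/m²).

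**The case against.** The best reply is that nobody would read the rules this way. Given the reason in 9.1.1, a site that refused a moderate CYP2C9 inhibitor and accepted a strong one would be acting against the evident purpose, and the intended meaning is almost certainly moderate or strong. The literal-reading clause governs eligibility only, so in 7.5.2 and 9.1.1 the change is one of consistency. This largely stands, and it is why the point is minor. It does not rescue 4.2.2.6, because a criterion that is to be read literally should not depend on inferred intent.

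On fluconazole, 7.3.2 already tells sites to avoid it, to avoid systemic antifungals unless a fungal infection is diagnosed, and to prefer topical agents. Calling it strong errs toward caution. If it is a moderate CYP2C9 inhibitor, 4.2.2.6 and 7.5.2 already prohibit it and only the rationale in 7.3.2 is wrong. Sections 4.2.3 and 4.2.8 also narrow the group who could enter on treatment for an infection, though not those on prophylaxis. All of this stands. The conflict between 7.3.2 and Appendix II remains.

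There are further safeguards: phosphate-driven holds (6.4), weekly chemistry in cycle 1 and repeated eye examinations (8.1), Study Chair notification before enrollment (3.5) and weekly leadership review (14.4.2). Apart from the Study Chair contact, these mostly detect a problem after exposure. They limit the harm but do not make the wording right.

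**Conclusion.** The point holds as a minor wording error in operative safety rules. As written, 4.2.2.6 does not exclude strong CYP2C9 inhibitors, 7.5.2 and 9.1.1 share the omission, and 7.3.2 and Appendix II disagree on fluconazole. These conclusions rest on the text alone.

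A reader might infer four stronger things, none of which the documents support.

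- **That a particular drug is let in.** The documents name no strong CYP2C9 inhibitor, so none is shown to pass through the gap.
- **That fluconazole is permitted.** The strong-only CYP3A4 bans do not reach it, but whether the CYP2C9 rules do cannot be settled, because the documents list no CYP2C9 inhibitors.
- **That exposure would become intolerable.** The inhibition range is assumed. At the nominal dose the results stay below 12 mg, and 12 mg is only a lower bound for the adult MTD. Reaching the 12 mg equivalent takes about 85% CYP2C9 inhibition, the same 50% rise that 7.6 accepts with monitoring. Upward rounding in the smallest patients would take the upper figure past 12 mg, but that too depends on the assumed inhibition.
- **That the smallest patients would lose treatment because of this wording.** Appendix IV offers no reduced dose at BSA 0.53 to 0.74 m², but that applies to toxicity from any cause. Phosphate of 7.0 to 9.0 mg/dL is managed in 6.4 by holding and restarting at the same dose, with reduction optional. No link to CYP2C9 inhibition or fluconazole is shown.

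The primary endpoint, the 20-patient design and its decision rule are unaffected.

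**What to change.** 1. In 4.2.2.6, in 7.5.2 and in the prohibition in 9.1.1, write 'moderate or strong inhibitors of CYP2C9'. Leave the sentence in 9.1.1 that reports raised exposure as it is, since it describes an observation.
2. In 7.3.2, give the rationale as 'strong or moderate inhibition of CYP3A4', which agrees with Appendix II. Keep the advice to avoid all four azoles.
3. In 7.5.1, add a cross-reference to the azole advice in 7.3.2. Word it so that it does not soften any ban on fluconazole that 7.5.2 may already impose. In particular, do not replace a possible prohibition with advice to avoid.

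The cost is a few words in four sections, with no new procedures, data or analyses. At most, a few patients may need a substitute drug.

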#### 7.4 Growth Factors

Growth factors that support platelet or white cell number or function can only be administered for culture proven bacteremia or invasive fungal infection. The Study Chair should be notified before growth factors are initiated.

#### 7.5 Concomitant Medications

- 7.5.1 CYP3A4 inhibitors or inducers: Strong CYP3A4 inhibitors or inducers are not permitted on study (See [Appendix II](#) for list of agents). Note: CYP3A4 inducing anti-epileptic drugs and dexamethasone for CNS tumors or metastases, on a stable dose, are allowed. No grapefruit juice, Seville oranges, or grapefruit can be consumed while on erdafitinib.
- 7.5.2 CYP2C9 inhibitors or inducers: Moderate CYP2C9 inhibitors or strong CYP2C9 inducers are not permitted on the study.
- 7.5.3 CYP3A4 substrates: Until further data become available, concomitant use of erdafitinib with CYP3A4 substrates with narrow therapeutic indices should be avoided.
- 7.5.4 Co-administration of erdafitinib with other serum phosphate altering agents may affect serum phosphate concentrations. Avoid co-administration of serum phosphate altering agents if reasonable alternatives exist.
- 7.5.4 Concomitant administration of erdafitinib with P-glycoprotein (P-gp) substrates may increase their systemic exposure if administered concurrently.
- 7.5.5 P-glycoprotein: Concomitant administration of erdafitinib with P-glycoprotein (P-gp) substrates may increase their systemic exposure if administered concurrently. Oral narrow therapeutic index P-gp substrates such as digoxin should be taken at least 6 hours before or after erdafitinib to minimize the potential for interactions
- 7.5.6 OCT2: Erdafitinib was shown to be an OCT2 inhibitor in vitro. Until further data are available, consider alternative agents that are not OCT2 substrates. Metformin is an example of an OCT2 substrate.

**7.6 Pharmacogenomic considerations**

The exposure of erdafitinib is predicted to increase by 50% in subjects with the CYP2C9 \*3/\*3 genotype. Therefore, monitor for increased adverse reactions in subjects who are known or suspected to have CYP2C9\*3/\*3 genotype. Dose changes are guided by serum phosphate levels in all subjects irrespective of genotype.

**8.0 EVALUATIONS/MATERIAL AND DATA TO BE ACCESSIONED**

**8.1 Required Clinical, Laboratory and Disease Evaluation**

All clinical and laboratory studies to determine eligibility must be performed within 7 days prior to enrollment unless otherwise indicated. Laboratory values used to assess eligibility (see [Section 4.0](#)) must be no older than seven (7) days at the start of therapy. Laboratory tests need **not** be repeated if therapy starts **within** seven (7) days of obtaining labs to assess eligibility. If a post-enrollment lab value is outside the limits of eligibility, or laboratory values are older than 7 days, then the following laboratory evaluations must be re-checked within 48 hours prior to initiating therapy: CBC with differential, bilirubin, ALT (SGPT) and serum creatinine. If the recheck is outside the limits of eligibility, the patient may not receive protocol therapy and will be considered off protocol therapy. Imaging studies, bone marrow aspirate and/or biopsy, must be obtained within 14 days prior to start of protocol therapy (repeat the tumor imaging if necessary).

STUDIES TO BE OBTAINED	Pre-Study	During Cycle 1	Prior to Subsequent Cycles^
History	X	Weekly	X
Physical Exam with vital signs	X	Weekly	X
Neurologic Exam	X		
Height, weight, BSA	X		X
Performance Status	X		
Pregnancy Test 	X		
CBC, differential, platelets	X	Twice Weekly (every 3 to 4 days) 	Weekly 
Urinalysis	X		
Electrolytes including Ca ++ , PO 4 , Mg ++	X	Weekly	X
Creatinine, ALT, bilirubin	X	Weekly	X
Albumin	X		X
Tumor Disease Evaluation 4-A, 4-B,	X		Every other cycle x 3 then q 3 cycles 
Bone Marrow Aspirate and/or biopsy 	X 		
EKG	X		
Ophthalmologic exam 	X	X	Every cycle during the first 4 cycles of treatment, then every 3 cycles afterward 
Plain radiograph tibial growth plate (Bone X-Ray Tests) 	X		Prior to cycles 2, 5 and every 6 months
Medication Diary 		Weekly	X
Pharmacokinetics (optional) 			
Circulating Tumor DNA (ctDNA- optional) 			Cycle 5, Day 1 and (for patients receiving ≥ 5 cycles

			only) at end of Protocol Therapy OR disease progression
--	--	--	---

- ^ Studies may be obtained within 72 hours prior to the start of the subsequent cycle.
- 1 Women of childbearing potential require a negative pregnancy test prior to starting treatment; sexually active patients must use an acceptable method of birth control. Abstinence is an acceptable method of birth control.
- 2 If patients have Grade 4 neutropenia then CBCs should be checked at least every other day until recovery to Grade 3 or until meeting the criteria for dose limiting toxicity.
- 3 If patients develop Grade 3 or greater thrombocytopenia then CBCs should be checked every 3 to 4 days until recovery per [Section 6.1](#).
- 4 Tumor Disease Evaluation should be obtained on the next consecutive cycle after initial documentation of either a PR or CR. Subsequent scans may restart 2 cycles after the confirmatory scan. If the institutional investigator determines that the patient has progressed based on clinical or laboratory evidence, he/she may opt not to confirm this finding radiographically.
- 4-A Neurological exam is also required for CNS patients.
- 4-B Non-Hodgkin Lymphoma/ Histiocytosis patients are required to have PET scans within 2 weeks prior to start of therapy and should also be followed with PET scans if positive at diagnosis. Refer to [Section 12.8](#).
- 4-C Patients with neuroblastoma must have both CT/MRI and MIBG scintigraphy prior to the start of therapy if the patient was enrolled with or has a history of having MIBG avid tumor. Otherwise the patient must have both CT/MRI and bone scan prior to the start of therapy. For patients with neuroblastoma and measurable disease by CT or MRI, lesions should be measured and followed using the same modality (CT or MRI) in addition to MIBG or bone scan. For patients with neuroblastoma and evaluable disease by MIBG scintigraphy or bone scan, use the same modality (MIBG scintigraphy or bone scan) to image and follow patients; CT/MRI are not required but may be performed as clinically indicated. Refer to [Section 12.5.4](#) and [Section 12.9](#).
- 5 Bone marrow aspirate and/or biopsy only required in patients suspected of having bone marrow metastasis on the basis of history, symptoms, laboratory evaluation or other clinical data.
- 6 Bone marrow aspirate and/or biopsy should be performed only when complete response or partial response is identified in target disease or when progression in bone marrow is suspected.
- 7 Medication diary (see [Appendix III](#)) should be reviewed weekly during cycle 1, after completion of each treatment cycle and uploaded into RAVE.
- 8 See [Section 8.4](#) for details of PK and plasma protein studies.
- 9 With consent, two samples will be collected on this protocol (Cycle 5 Day 1; and for patients receiving  $\geq 5$  cycles, at progression or end of protocol therapy) see [Section 8.5](#) for details of the ctDNA studies. Note that a ctDNA sample is scheduled to be obtained on the APEC1621SC screening protocol prior to the initiation of treatment on this subprotocol.
- 10 Patients are required to have a baseline ophthalmological exam including fundoscopy, prior to the first dose of study medication, patients with significant ophthalmologic exams should refer to [Section 4.2.9](#). Additionally, an ophthalmological exam should be performed every cycle for the first 4 cycles of treatment, then every 3 cycles afterward.
- 11 Plain radiographs of at least one tibial growth plate should be obtained in all patients prior to first dose of protocol therapy. In patients with open growth plates, follow-up plain radiographs of the same growth plate(s) should be obtained according to [Section 8.2.1](#).

